- Total and non-HDL cholesterol measured at clinical patient visits during the follow up period
- Changes in antidiabetic, cholesterol, and blood pressure management medications during the follow up period
- Number of visits during the follow up period
- Healthy lifestyle goals as entered by a patient and/or care team members into the MyChart portal
- Patient message reports for study-specific outbound messages*
- Individual questionnaire responses for study-specific MyChart questionnaires*
- Information about patterns of an individual's use of a wireless home body weight scale, along with the date/time and value of each recorded weight that is transmitted to the Epic electronic health record system during the evaluation period*

**Not applicable to no-intervention comparison arm patient participants.*

QUALIFICATIONS TO CONDUCT RESEARCH AND RESOURCES AVAILABLE

Our research team is multi-disciplinary and experienced in areas of health promotion, disease prevention, health communication, health behavior, and sustainable implementation of evidence-based programs and services to prevent and manage chronic conditions across primary care and community settings. **[name]** has 15 years of experience in stakeholder-engaged health promotion and disease prevention research focusing on the sustainable implementation of evidence-based lifestyle interventions spanning primary care and the community. **[name]** is a health communications expert with extensive expertise in qualitative research and survey design. **[name]** is a behavioral scientist with expertise in the implementation of theory-driven health promotion interventions that span the interface of healthcare practice and community settings. **[name]** is an expert in evaluating health care professional and delivery system interventions using experimental, quasi-experimental, and qualitative research designs. **[name]** has considerable experience in the management and analysis of large multi-source healthcare and public health data sources. Research assistants and other project coordination and management staff have completed CITI training and good practice, such as in areas of the proper collection of informed consent, data collection and entry, and how to manage adverse events (both anticipated and unanticipated) in the course of routine research.

Because the proposed trial is a pilot and feasibility study, we have chosen a sample size needed to design the intervention to be implemented and sustained within routine practice workflows and to be usable to patients. Primary care practices in the Northwestern Medical Group (NMG) central region deliver care to more about 183,000 unique adult patients annually. Our pilot study will take place at the Galter Primary Care (GPC) site, which is relatively close to the medical campus and sees a patient case mix that mirrors the larger NMG patient population. About 70% of GPC patients have used MyChart in the past year, and 32% of those (N=5,967) meet the study's eligibility criteria. Thus, recruitment of the proposed sample will be feasible.

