The novel combination of existing lifestyle intervention components resulting from phase 1 of the research will subsequently be evaluated using a pragmatic randomized intervention design. The goal of this research is to evaluate the new cluster of interventions, which we call Coordinating Pragmatic Primary care Population management for Obesity (C3PO), among a sample of patients who are representative of all patients who might be offered the intervention in routine practice. Thus, instead of recruiting highly selected research volunteers for the pilot trial, we will use a pragmatic randomization design that will use a “behind the scenes” randomization approach to assign 80 eligible patients to receive Basic Resources and Services for healthy lifestyle support (n=40) or the C3PO pilot intervention (n=40). We will not collect data for research purposes only in this trial. Rather, we will use routinely collected clinical data (i.e. available from the electronic health record) for each patient. Following completion of the 4-month pilot trial phase, we will then recruit and consent 20 patients who were eligible for the intervention to complete semi-structured interviews to assess patient experiences, perceptions, and barriers faced during the intervention period. This final step will help to inform any additional relevant intervention refinements prior to conducting a larger and more definitive future trial of the intervention’s effectiveness.

Figure 1. Development & Pre-Testing of a Novel Intervention for Coordinating Pragmatic Primary care Population management for Obesity (C3PO)

THE INTERVENTION DEVELOPMENT PHASE HAS 4 GENERAL OBJECTIVES:

- 1) **ASSESS HEALTHCARE PROVIDER PERCEPTIONS REGARDING C3PO INTERVENTION NEEDS, PRIORITIES, AND PREFERENCES**
- 2) **ASSESS EXISTING RESOURCES & WORKFLOWS**
- 3) **INTEGRATE EXISTING WORKFORCE, WORKFLOW, AND IT COMPONENTS NEEDED FOR POPULATION HEALTH MANAGEMENT TO BE EFFICIENT AND EFFECTIVE**
- 4) **PRETEST IT COMPONENTS USING LIMITED PATIENT USABILITY TESTING**

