- 2) **Self-monitoring of Body Weight:** Prior research suggests that process accountability (e.g. accountability over self-weighing) increases completion of a target behavior even more than outcome accountability alone (e.g. accountability over achieving a weight loss goal).¹³ Self-weighing is a form of behavioral self-monitoring that past research has found to be strongly predictive of weight loss success.¹² C3PO will provide each patient with a BodyTrace electronic scale (eScale), which transmits weight data wirelessly to a secure, private repository using digital mobile telecommunications technology (i.e. the same cellular networks as a smartphone). The manufacturer reports accuracy within +/-0.1 kg to a weight limit of about 150 kg (330 lbs.).⁸¹ This approach, used in prior research by our group,⁸² also enables the seamless integration of self-weighing information back into the EpicCare EHRS (i.e. back to the registry as well as to the PHM nurse). This integration will allow dynamic individualized feedback from the nurse back to each patient in a way that further strengthens supportive accountability and progress toward weight goals. More details are provided below.
- 3) **Supportive Accountability for Achieving Self-management Goals and Objectives:** Nurse-patient interactions, largely facilitated by the patient portal, will be designed to strengthen each patient's commitment toward their goal, as well as a greater sense of "**supportive accountability.**" Accountability toward a behavior exists when an individual has an expectation that he/she may be called upon to justify his/her actions or inactions to another person.¹³ Accountability requires real or perceived social interactions with another human (i.e. a coach) who the patient views as trustworthy and possessing suitable expertise. This relationship may be established in person, by telephone, or via an electronic channel. C3PO will utilize secure patient-facing EHRS technologies to deliver recommendations of the patient's own primary care provider via the practice team's PHM nurse. For patients who request additional information or assistance in goal setting or decision making, the PHM nurse will offer a telephone or face-to-face encounter as an alternative. The planned approaches for supporting goal setting, self-monitoring, and intensive intervention linkages are described further below.

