- 4) **Linkages to Evidence-based Lifestyle Interventions:** Once patients have set a goal and begun using their eScale, the PHM intervention will utilize MyChart messaging to offer a selection of links to

available lifestyle programs and services, with brief summary information about benefits and attributes to help in making choices among them, or to facilitate a request for additional information or assistance from the PHM nurse. Based on the key characteristics of evidence-based intensive lifestyle programs,^{12,14} we have identified an array of extant lifestyle interventions to include in a menu of initial program choices for each patient.

- 5) Targeted, Person-centered Follow-up Support:** The PHM framework attempts to provide basic support to all patients and uses “lighter touches” with patients who are engaged and having success; more intensive support is reserved for patients who are less successful. C3PO will use the frequency and results of self-weighing to stratify patients to different forms of support. Immediately after a patient sets a weight goal, the PHM nurse will ship him/her an eScale and welcome package, including additional support materials and instructions for initializing the scale and registering a first body weight. If there is no weight received from the eScale within 1 week, the patient will receive a short message offering assistance or to talk to the nurse for help troubleshooting technical issues or revisiting action planning steps if engagement has diminished. Patients who do register their first weight will receive a MyChart message offering praise and relisting a short menu of linkages where the patient can find further information about evidence-based community programs. All messages will also offer an option of telephonic support from the PHM nurse.

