1. Are you...

Male Female Transgender Prefer not to respond

2. What is your specific title: _____

3. Year you completed training: _____

4. Year you began current employment at Northwestern: _____

Research Activity #2: Each patient participant (n=10) will take part in a 60 to 90-minute videotaped session during which they will go through all steps of the logging in, opening the MyChart message, entering responses to the goal setting / action planning survey prompts, and navigating community resource links and other associated patient decision support. [name] and [name] will facilitate and observe all usability testing, noting preferred navigation paths and the nature of any errors or sources of confusion. Noldus software will record user-system interaction (i.e., logging mouse click, keystrokes) and will organize the data and analyses. After the first three participants, [name] and [name] will meet with the Epic programmers to review key findings and refine the system interfaces to enhance usability. After the second wave, any remaining enhancements to optimize workflow integration will be made before launch of the future pilot trial.

THE INTERVENTION EVALUATION PHASE HAS 2 GENERAL OBJECTIVES:

- 1) CONDUCT A PILOT INTERVENTION TRIAL ASSESSING FEASIBILITY AND PRELIMINARY EFFECTS SIZES FOR THE IMPLEMENTATION STRATEGY/INTERVENTION.**
- 2) REFINE INTERVENTION IMPLEMENTATION APPROACHES PRIOR TO DESIGNING A FUTURE MORE DEFINITIVE EFFECTIVENESS TRIAL**

INTERVENTION EVALUATION OBJECTIVE 1: CONDUCTING THE PILOT TRIAL: The pilot trial will include 2 general research activities that are designed to assess feasibility and preliminary reach and effectiveness of the intervention implementation approaches. Findings of the evaluation will be used to inform intervention refinements prior to designing and conducting a future larger scale effectiveness trial.

RESEARCH ACTIVITIES INCLUDED DURING THE PILOT TRIAL:

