Research Activity #3: For the pilot intervention trial, each patient participant will be randomized to receive either Basic Resources and Services or the C3PO intervention. Patients assigned to Basic Resources and Services (BRS) will receive approaches 1-4 described in detail above in **Objective 3, “Patient-Facing IT Development”** which include 1. Individualized goal setting, 2. Self-monitoring of body weight, 3. Supportive accountability for achieving self-management goals and objectives and 4. Linkages to evidence-based lifestyle interventions. Patients assigned to C3PO will also receive BRS approaches 1-4 described above as well as approach 5. Targeted, person-centered follow up support. From among all patients who are deemed eligible but who are not recruited, a no-intervention comparison group of 80 additional patients also will be selected for additional comparisons. Routinely collected clinical data for participants will be analyzed after trial completion.

Research Activity #4: After the pilot phase, 20 semi-structured interviews will be completed by the study team with eligible patients to assess patient experiences, perceptions, and barriers faced during the intervention period.

SHARING RESULTS WITH PARTICIPANTS

Study results and individual participant results will not be shared with participants or anyone else. Only the PI can give permission for the release of aggregated study data. No confidential information will be released without the expressed written consent of the study participants.

STUDY TIMELINES

Table 1. Timeline for Steps of Intervention Development

Milestone	Q1	Q2	Q3	Q4
Weekly meetings of core research team	X	X	X	X
Kick off presentation at practice monthly business meeting	X			
Biweekly meetings with practice director and population health nurse	X	X		
Clinical provider interviews (n=15)	X	X		
Focused pretesting of outreach message content with patients		X	X	
Finalize language of outreach messages & action planning algorithms			X	
Programming of action planning items for collection in the EHRS patient portal			X	
Usability tests of patient-facing survey navigation and goal setting functions (n=10)			X	X
Assist NMG Epic IT to integrate health IT into their OW/OB patient registry	X	X		
Complete integration of electronic Scale data feeds into registry		X	X	
Develop patient registry tracking dashboard for PHM nurse view		X	X	
“Dry” runs of all health IT components with dummy patients				X

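### Does the pilot miss its stated goal because both randomized arms receive four of the five C3PO components?

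*Protocol*

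**What the plan says.** **Goal.** Protocol, Phase 2: Intervention Evaluation, says the combination of components "will subsequently be evaluated using a pragmatic randomized intervention design", and adds: "The goal of this research is to evaluate the new cluster of interventions, which we call" C3PO. The next sentence assigns 80 patients, 40 to BRS and 40 to C3PO. The section closes by placing this work "prior to conducting a larger and more definitive future trial". General objective 1 of the evaluation phase promises feasibility results and "PRELIMINARY EFFECTS SIZES FOR THE IMPLEMENTATION STRATEGY/INTERVENTION".

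**Arms.** Research Activity #3 gives BRS components 1 to 4: goal setting, self-weighing, supportive accountability and programme linkages. It then says: "Patients assigned to C3PO will also receive BRS approaches 1-4 described above as well as approach 5", which is targeted follow-up. It also sets aside 80 eligible but unrecruited patients as a no-intervention group for additional comparisons.

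**Component text.** Patient-facing IT Development, item 2 (shared), supplies the eScale and says of the data link: "This integration will allow dynamic individualized feedback from the nurse back to each patient". It then points to details further on. Item 5 (C3PO only) says: "Immediately after a patient sets a weight goal, the PHM nurse will ship him/her an eScale and welcome package", and sets out the weekly classification and the messages that depend on it. The SAP, Data Sources & Collection, says all participants were given an eScale at randomization.

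**Analysis.** The SAP, Statistical Analysis, compares the two randomized arms on the primary outcome by chi-square or Fisher exact test.

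**The concern.** Two things catch the eye.

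First, a reader who takes the goal sentence at face value expects the effect of the five-part package. Randomization delivers the effect of the fifth part on top of the other four. If the C3PO minus BRS difference were later quoted as the package effect, a future trial with some other comparator would be planned on the answer to a different question. The Protocol does not name that trial's comparator.

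Second, the component text does not draw the line between the arms cleanly. Scale shipment is described inside the C3PO-only item, and nurse feedback on weights is mentioned inside a shared item. If BRS patients received much the same weight-driven contact, a small difference between arms would be hard to read. It might mean that targeted follow-up adds little, or that the arms were barely separated.

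**Working it through.** **1. The plan's own figures.** The randomized total reproduces: 40 + 40 = 80. Targeted accrual also reproduces: 15 professionals + 10 usability patients + 80 randomized + 20 interviewees + 80 no-intervention = 205. The no-intervention group is thus additional to the randomized 80. The available text contains no power statement, and the sample size is justified on feasibility.

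**2. What randomization identifies.** C3PO is {1, 2, 3, 4, 5} and BRS is {1, 2, 3, 4}. The difference is {5}, given 1 to 4. Recruitment Methods for Research Activity #3 points the same way, since patients affirm weight-loss interest and goals before being randomized. Four of five headings are common to both arms, but that is a count of headings. It says nothing about how much of any effect each carries.

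**3. Does the plan claim more than that?**
- The goal sentence is followed at once by the two arms.
- Research Activity #3 states the contrast component by component.
- The PHI and HIPAA section restates the goal as assessing the reach and effectiveness of implementation strategies for preventive services. Study Activities, Phase 1, says goal setting, brief counselling and linkages are already part of practice guidelines. Sharing those elements and randomizing the added follow-up fits that aim.
- No available sentence calls the C3PO minus BRS difference the effect of the package against nothing.

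**4. Where the arms separate.**

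| Element | Shared items | Item 5 (C3PO only) | Reading |
|---|---|---|---|
| eScale | Supplied in item 2; item 4 presupposes its use | Shipment described | Both arms; the SAP confirms it |
| Nurse telephone support | Offered in item 3 | Offered with all messages | Available on request in both arms |
| Weight-driven messages | Item 2 says the data link will allow nurse feedback and defers the details | All the operating rules | C3PO only on the natural reading; not stated for BRS |

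Only the last row stays open. The component text uses the name C3PO even for shared items, which suggests that it describes the programme as a whole and that its item boundaries were not drafted as arm boundaries.

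**5. Would clarification alter a result?** The estimate is the C3PO proportion minus the BRS proportion among all randomized patients. The data and the test are the same whichever way the goal sentence is worded. The SAP dates every randomization between 12/16/2019 and 1/6/2020, and the Protocol version is dated July 1, 2020, so wording cannot change which arm anyone was assigned to.

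**6. Could the pilot difference mislead planning by itself?** The documents give no outcome rates, so this is illustration only. Assume 25% success with C3PO and 10%, 15% or 20% with BRS. The 95% half-width is 1.96 × √[(p₁(1−p₁) + p₂(1−p₂))/40]:
- 25% vs 10%: 1.96 × √[(0.1875 + 0.0900)/40] = 16.3 points, against a difference of 15
- 25% vs 15%: 1.96 × √[(0.1875 + 0.1275)/40] = 17.4 points, against 10
- 25% vs 20%: 1.96 × √[(0.1875 + 0.1600)/40] = 18.3 points, against 5

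In each case the interval is wider than the difference, so the pilot estimate alone is a weak basis for sizing a trial with any comparator.

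**The case for a change.** The best case for a change is that it costs little and addresses a real gap. The goal and objective 1 speak of the intervention, and no available sentence states that the randomized estimate is the increment from component 5. The no-intervention group cannot supply the package effect. It is not randomized, it is selected for similar age and sex only, and it is uncontacted, whereas trial patients had affirmed interest in weight loss. Feedback driven by eScale data is the core of component 5, so silence about BRS leaves even the narrower contrast blurred at its edge.

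Much of this is accurate. The contrast is the increment, the no-intervention comparison is open to selection bias, and the feedback point is not spelled out. It does not follow that the plan must change. The arms are disclosed, so an analyst or reader can name the contrast from Research Activity #3 alone. The Protocol already calls the no-intervention comparison additional and retrospective. On feedback, the shared item describes a capability and defers the details, and those details sit in the item that Research Activity #3 gives to C3PO only. The data that would show separation are already within the plan: study-specific message reports are listed under PHI and HIPAA, and the SAP uses nurse contacts to estimate staff time by arm.

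**Conclusion.** No change is needed. The trial compares C3PO (components 1 to 5) with BRS (components 1 to 4) and so estimates the increment from component 5. That is a legitimate add-on design, openly described, and a C3PO-versus-BRS conclusion drawn under the plan as written would be sound. Feasibility, reach, cost and patient experience are unaffected.

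What remains is a minor matter of description: whether BRS patients receive nurse feedback driven by eScale data. Items 2 and 5 and Research Activity #3 need to be reconciled on that point when the trial is reported. Messages and nurse contacts tabulated by arm would show how far the arms separated. The effect on any planned test, estimate or sample size is nil.

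This rests on the text available. Figure 1 and the part of the SAP ahead of the Analysis Plan heading were not, and either may already state the comparison. It also assumes that the report will describe the difference as C3PO against BRS and not as the package against no care.
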